4.3.3 Treatment Details – Arm A: Axitinib + Nivolumab

Each cycle lasts 28 days (4 weeks). Absent disease progression or unacceptable toxicity, patients may continue on protocol therapy for up to 2 years duration or completion of 26 cycles, whichever comes first.

For patients who cross-over at disease progression on Arm C prior to Cycle 22, prior cycles received are included in total therapy calculations permitted on study.

Criteria to start each cycle: ANC \geq 1000/ μ L, platelet count \geq 75,000/ μ L without transfusion support. See [Section 5.0](#) for other requirements related to any ongoing toxicities.

Axitinib: PO

Days: 1 – 28

Dose: Age-based dosing as follows:

If \geq 18 years old: 5 mg/dose BID*

If $<$ 18 years old: 2.4 mg/m²/dose BID (maximum starting dose of 5 mg/dose)*. See [Appendix IV](#) for axitinib dosing nomogram and titrations.

NOTE: Dose is BID. For example, if age $<$ 18 years old administer 2.4 mg/m²/dose BID. The total daily dose is 4.8 mg/m²/day, divided BID (maximum starting dose is 5 mg/dose BID).

Axitinib should be taken by mouth twice daily approximately 12 hours apart. Axitinib may be taken with or without food. Tablets should be administered whole and intact with a glass of water or other liquid; do not crush or cut tablets. If a dose is missed or vomited, the patient/subject should not try to repeat or “catch up” the dose. The next dose should be given at the next regularly scheduled time point.

Axitinib will be distributed by the Division of Cancer Treatment and Diagnosis (DCTD), NCI. Do not use commercial supply.

***Axitinib dose titration:**

Individual patient dose titration of axitinib (escalation from starting dose) is permitted on protocol therapy, at the discretion of the treating physician, if the following criteria are met for an individual patient:

1. Two consecutive cycles are completed at a given dose without any adverse reactions $>$ Grade 2 (according to the Common Toxicity Criteria for Adverse Events [CTCAE]).
2. The patient is normotensive, and not receiving anti-hypertension medication.

For patients \geq 18 years old, when a dose increase from 5 mg twice daily is recommended, the axitinib dose may be increased by 1 mg/dose twice daily (for example, from 5 mg twice daily to 6 mg twice daily, etc), up to a maximum of 10 mg twice daily. No more than 1 dose titration can occur in each 2-cycle period per the criteria above. Refer to the table in [Section 5.2.1.1](#) for additional detail.

For patients < 18 years old, see [Appendix IV](#) for dose titration nomograms. No more than 1 dose titration can occur in each 2-cycle period per the criteria above. The maximum titration dose is as per the Dose Level 3 table in [Appendix IV](#).

Nivolumab: IV over 30 minutes, or per institutional guidelines

Age	Dose and Days
≥ 18 years old	Either 240 mg/dose on Days 1 and 15 OR 480 mg/dose on Day 1 only
< 18 years old	3 mg/kg/dose (maximum 240 mg/dose) on Days 1 and 15

The risk of infusion reactions with nivolumab is low and no pre-medications are required. Monitoring for infusion reactions should be per institutional guidelines. Please refer to [Section 5.3.2](#) for suggested infusion reaction management guidelines.

Nivolumab will be distributed by the Division of Cancer Treatment and Diagnosis (DCTD), NCI. Do not use commercial supply.

See [Section 5.0 for Dose Modifications based on Toxicities.](#)

Following completion of a cycle, begin next cycle on Day 29 or when criteria to begin cycle are met, whichever occurs later.

4.4 Arm B: Axitinib (For patients enrolled and randomized to Arm B prior to Amendment 2A) Closed to new accrual with Amendment 2A

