- HIV-infected patients with the exception of patients on an effective anti-retroviral therapy with an undetectable viral load within 6 months prior to enrollment.
- Patients with underlying hematologic issues including congenital bleeding diathesis, known previous GI bleeding requiring intervention within the past 6 months, history of hemoptysis within 42 days prior to study enrollment, active pulmonary emboli, or deep vein thromboses (DVT) that are not stable on anticoagulation regimen.
- Patients must not have had significant vascular disease (i.e. Moya-Moya, aortic aneurysm requiring surgical repair).
- A known history of, or any evidence of active, non-infectious pneumonitis.
- Patients with known active central nervous system (CNS) metastases and/or carcinomatous meningitis or leptomeningeal disease. Patients with previously treated brain metastases may participate provided they are stable (without evidence of progression by imaging for at least 4 weeks prior to study enrollment and any neurologic symptoms have returned to baseline), have no evidence of new or enlarging brain metastases, and are not using steroids for at least 7 days prior to study enrollment. This exception does not include carcinomatous meningitis which is excluded regardless of clinical stability.
- Any uncontrolled, intercurrent illness including but not limited to ongoing or active infection, symptomatic congestive heart failure, unstable angina pectoris, cardiac arrhythmia.

- Any serious medical or psychiatric illness/condition including substance use disorders likely in the judgment of the Investigator(s) to interfere or limit compliance with study requirements/treatment.
- Patients with active autoimmune disease that has required systemic treatment in the past 2 years (i.e. with use of disease modifying agents, corticosteroids or immunosuppressive drugs). Replacement therapy (e.g., thyroxine, insulin, or physiologic corticosteroid replacement therapy for adrenal or pituitary insufficiency, etc.) is not considered a form of systemic treatment.

3.2.8.5 Treatments and/or medications the patient is receiving or has received that would make her/him ineligible, including:

- Concomitant (or receipt of) treatment with medications that may affect the metabolism of nivolumab and/or axitinib within 7 days prior to planned first dose of protocol therapy.

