5.1.1 Hematological DLT

5.1.1.1 Hematological dose-limiting toxicity is defined as:

- Grade 4 thrombocytopenia (platelet count $< 25,000/\mu\text{L}$) or Grade 4 neutropenia for > 7 days (see [Section 5.2](#)), not due to malignant infiltration.

5.1.1.2 Other hematological dose-limiting toxicities:

- Any Grade 2 arterial thromboembolic events (including cerebrovascular ischemia, peripheral or visceral arterial ischemia).
- Any \geq Grade 3 venous thromboembolic event.
- Any thrombotic event requiring systemic anti-coagulation.
- Any \geq Grade 2 hemorrhage.

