5.1.2 Non-hematological DLT

5.1.2.1 Any Grade 3 or Grade 4 non-hematological toxicity attributable to the investigational drug with the specific exclusion of:

- Grade 3 proteinuria (urine protein/ creatinine (P/C) ratio > 1.9 for age < 18 ; urine protein $\geq 3.5 \text{ g}/24 \text{ hours}$ for age 18 and greater) unless it is confirmed with a second measurement within 72 hours.
- Grade 3 liver enzyme elevation, including AST/ALT that returns to levels that meet eligibility criteria within 7 days of study drug interruption and that does not recur upon study drug rechallenge.
- Grade 3 GGT, if checked. (Note: monitoring GGT is not required for this study)
- Grade 3 serum electrolyte elevation that returns to baseline within 7 days and does not require systemic immunosuppression.
- Grade 3 asymptomatic lipase elevation that resolves to meet the eligibility criterion within 7 days of study drug interruption and that does not recur upon study drug re-challenge.
- Grade 3 or 4 amylase or lipase abnormalities that are not associated with diabetes mellitus (DM), associated liver or gall bladder inflammation clinical manifestations of pancreatitis and which decrease to \leq Grade 2 within 7 days.
- Grade 3 diarrhea ≤ 3 days duration.
- Grade 3 nausea and vomiting of less < 3 days duration.
- Grade 3 or 4 fever < 5 days duration.
- Grade 3 infection < 5 days duration.
- Grade 3 rash/oral lesion that resolves to Grade ≤ 1 within 7 days.
- Fever greater than 40°C of ≤ 24 hr duration.
- Grade 3 fatigue that resolves to Grade ≤ 2 within 7 days.

- Grade 3 creatinine increased that resolves to Grade ≤ 1 or baseline within 7 days.
- Grade 3 pleural effusion that resolves per [Section 5.2.6](#).
- Grade 3 hypophosphatemia, hypokalemia, hypocalcemia or hypomagnesemia responsive to oral supplementation.

5.1.2.2 Grade 2 uveitis, eye pain, or blurred vision that does not respond to topical therapy and does not improve to Grade 1 prior to the next scheduled dose.

5.1.2.3 Grade 2 non-hematological toxicity requiring systemic immunosuppressive therapy, including but not limited to, autoimmunity of the lung, heart, kidney, bowel, CNS, pituitary or eye, with the specific exclusion of:
a. Grade 2 pleural effusion that resolves per [Section 5.2.6](#).
b. Drugs will be held for Grade 2 cardiac dysfunction pending evaluation.

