5.1.2.4 Grade 2 endocrine toxicity requiring hormone replacement, with the exception of Grade 2 hypothyroidism, thyroiditis, and thyroid dysfunction adequately managed with thyroid hormone replacement (see [Section 5.3](#)).

5.1.2.5 Grade 2 adrenal insufficiency.

5.1.2.6 Grade 2 colitis or Grade 2 diarrhea attributable to protocol therapy that persists for > 7 days.

5.1.2.7 Any non-hematological toxicity requiring > 7 days delay in therapy.
NOTE: Allergic reactions that necessitate discontinuation of study drug will not be considered a DLT.

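### Axitinib titration criterion 1 does not exclude a Grade 2 bleed or arterial event that Section 5.1 calls dose-limiting, so a normotensive patient off antihypertensives can still qualify for a higher dose

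*Combined protocol and SAP*

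**What the plan says.** **Titration.** Section 4.3.3 permits axitinib escalation at the treating physician's discretion on two criteria. The first is "Two consecutive cycles are completed at a given dose without any adverse reactions $>$ Grade 2". The second is normal blood pressure without antihypertensive medication. Adults go up by 1 mg per dose, children follow the Appendix IV nomograms, and only one step is allowed per two-cycle period. Patients who cross over from Arm C receive Arm A therapy, so 4.3.3 governs them too. Section 4.4.3 repeats the criteria for Arm B, closed to accrual since Amendment 2A.

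**Dose-limiting toxicity.** Section 5.1 counts a listed event as a DLT when it is at least possibly attributable to protocol therapy. Section 5.1.1.2 lists "Any Grade 2 arterial thromboembolic events (including cerebrovascular ischemia, peripheral or visceral arterial ischemia" and, with a greater-than-or-equal sign in front, "Grade 2 hemorrhage". The only action that the opening of 5.1 attaches to a DLT is to notify the Study Chair.

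**Axitinib holds and reductions.** Section 5.2.3 is triggered by Grade 4 neutropenia or thrombocytopenia, and 5.2.4 by Grade 3 or 4 non-hematologic toxicity.

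**The concern.** The titration rule and the DLT definitions use different grade thresholds, and nothing connects them. Criterion 1 accepts anything up to and including Grade 2, while 5.1.1.2 treats two kinds of event as dose-limiting from Grade 2. An event serious enough to be called dose-limiting therefore does not, on the wording, stop the dose from going up.

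Bleeding terms and arterial thromboembolism are in the rare-but-serious column of the axitinib risk list (CAEPR) in Section 6.1. In the pediatric phase 1 study ADVL1315 (Section 2.3), DLTs occurred in 0 of 6 patients at 2.4 mg/m²/dose and 2 of 5 at 3.2 mg/m²/dose. One of the two was an intratumoral hemorrhage, with no grade given. Those numbers are too small to estimate a rate, but they show why a bleed should count when a higher dose is considered.

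The protocol does use DLT status in nearby decisions. Section 5.2.2 reserves elective axitinib breaks for toxicities that are not DLTs. Section 10.2.1 requires the absence of a DLT before treatment continues through possible pseudoprogression, although that is a different decision.

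**Working it through.** The main check is a comparison of rules. The arithmetic only sets the scale.

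**1. Does a Grade 2 event fail either criterion?** Criterion 1 excludes grades above 2, and Grade 2 is not above 2, so it passes. Criterion 2 concerns only blood pressure and antihypertensive drugs, so a normotensive, untreated patient passes. Both criteria are met.

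**2. Does another rule close the gap?**

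| Rule | Reaches a Grade 2 bleed or arterial event? |
|---|---|
| 5.1, Study Chair notification | Yes, if suspected or confirmed as a DLT, but it sets no dosing consequence |
| 5.2.3, 5.2.4 | No; they start at Grade 4 counts and Grade 3 non-hematologic toxicity |
| 5.2.5 to 5.2.9 | No; they cover hypertension, effusion and ascites, proteinuria, cardiac toxicity and diarrhea |
| 5.2.3.1, no re-escalation | Only after a dose was reduced for toxicity; 5.2 requires no reduction for these events |
| 5.3.4 | Only by investigator judgment of substantial risk; it sits in the nivolumab section |
| 8.1(i), 8.1(k) | By judgment; 8.1(i) points to Section 5.0, which does not list these Grade 2 events as grounds for removal |

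No rule expressly bars titration after such an event.

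**3. How large is the step, and how early?** Adults: 6/5 mg twice daily = +20%. Children, Appendix IV total daily dose, Level 2 over Level 1 by rising BSA band: 4/3, 5/4, 6/5, 8/6, 9/7, 10/8, 11/9, 12/10, or +33, +25, +20, +33, +29, +25, +22, +20%. Earliest titration: 2 × 28 = 56 days.

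**4. Where does titration take a child?** Divide half the total daily dose by BSA, over the bands with an upper BSA limit. Level 2 runs from 3/1.14 = 2.6 to 2/0.53 = 3.8 mg/m²/dose, which spans the 3.2 mg/m²/dose tested in ADVL1315. The lowest Level 3 value is 3/0.93 = 3.2. Section 2.7 confirms that escalation beyond the ADVL1315 doses is allowed.

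**5. How many patients?** Inputs: target accrual of 28 (Section 9.1), 1:1 randomization (9.2), and the <3% column heading in the axitinib CAEPR (6.1).

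- Arm A only: 28/2 = 14 patients; 14 × 0.03 = 0.42, so under 0.42 patients per term.
- All Arm C patients crossing over: 28 × 0.03 = 0.84, so under 0.84 per term.

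These are ceilings at any grade. They come before requiring Grade 2, timing in the qualifying cycles, attribution, normal blood pressure off medication, and a physician who chooses to escalate.

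**The case against.** **The case for leaving it.** The criteria are minimum conditions for a clinical judgment and entitle nobody to a higher dose. Few physicians would raise a VEGFR inhibitor after an attributable bleed or arterial event, and the Study Chair should have been told. The cut-off matches the earlier titration criteria in Section 2.2.1, which excluded Grade 3/4 axitinib-related toxicity. This protocol is stricter than those on duration (two 28-day cycles against at least 2 weeks) and on antihypertensives (none against up to two). The DLT definitions come from two phase 1 studies and serve the Cycle 1 monitoring rule in 9.5, so a different threshold for another purpose is not in itself a contradiction.

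Most of this stands, and it is why the point is small. But written criteria exist to limit discretion, and the stricter duration and blood pressure conditions do not address these Grade 2 events.

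**Stronger readings that a reader might infer.**

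- *Any Grade 2 bleed or arterial event leaves a patient eligible for titration after a DLT.* No. The blood pressure criterion must also be met, and the event is a DLT only if at least possibly attributable to protocol therapy.
- *Every Grade 2 DLT in Section 5.1 shows the same gap.* The literal mismatch recurs in 5.1.2.2 to 5.1.2.6 and 5.1.2.9, for example "Grade 2 non-hematological toxicity requiring systemic immunosuppressive therapy" and "Grade 2 endocrine toxicity requiring hormone replacement". These are mostly immune-type or persistent events, and some have their own rule: Table 2 has Grade 2 holds of nivolumab for diarrhea or colitis. Where treatment was interrupted, it is open whether two cycles were completed at the given dose.
- *Anticoagulated thrombosis belongs with the two main events.* "Any thrombotic event requiring systemic anti-coagulation" has no grade floor, so the gap there is only inferred. Section 3.2.8.4 excludes at entry only "deep vein thromboses (DVT) that are not stable on anticoagulation regimen", so a stable DVT on anticoagulation is accepted.
- *Several patients will be affected.* Adding the ceilings of six bleeding or arterial terms gives 6 × 0.42 = 2.5 to 6 × 0.84 = 5.0. That sum puts every term at 3%, at any grade, with no overlap, and its upper end has every Arm C patient crossing over. It is not an estimate.

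**Conclusion.** The gap is real on the text but narrow. It rests on two event types, Grade 2 hemorrhage and Grade 2 arterial thromboembolism, in patients who also meet the blood pressure criterion and whose event is at least possibly attributable to protocol therapy. The expected number is very small: under about 0.4 to 0.8 patients per term before the further conditions. That scale assumes that the <3% heading covers all grades, that accrual is 28, and that single-agent axitinib frequencies carry over; Section 6.1 warns that combinations could worsen known events.

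A reader might infer a threat to the trial's conclusions. The documents do not support that. Alpha, power, the event count and the PFS comparison do not depend on this rule, and the 9.5 boundary counts first-cycle events, before any titration is possible. This is a patient-safety wording gap worth closing at the next amendment.

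**What to change.** In Section 4.3.3, keep criterion 1 and add after its grade condition: *and without any DLT (Section 5.1) at least possibly attributable to axitinib*. This is where the change has practical effect, for Arm A patients and Arm C crossovers. Make the same edit in 4.4.3 so that the two sections agree; with Arm B closed, it may affect nobody.

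No new hold rule is proposed. Whether a patient should stay at the same dose after such an event is a separate question, left to existing judgment. No new data are needed, because 11.10 already requires routine reporting of all DLTs.

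The cost is one clause in two places, carried through an amendment. The few affected patients must complete at least two further cycles (2 × 28 = 56 days) without such a DLT, counted from the end of the cycle in which the event occurred, before titration. After that they can qualify again.

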4.4.1 Therapy Delivery Map – Arm B: Axitinib

Each cycle lasts 28 days (4 weeks). Absent disease progression or unacceptable toxicity, patients may continue on protocol therapy for up to 2 years duration or completion of 26 cycles, whichever comes first.

This TDM is on 3 pages. A copy of this TDM will be used for each cycle; please enter the cycle # below.

Criteria to start each cycle: ANC \geq 1000/ μ L, platelet count \geq 75,000/ μ L without transfusion support. See [Section 5.0](#) for other requirements related to any toxicities.

DRUG	ROUTE	DOSAGE	DAYS	IMPORTANT NOTES
Axitinib (IND# [REDACTED]) Do not use commercial supply	PO	If \geq 18 years old: 5 mg/dose BID ⁺ If < 18 years old: 2.4 mg/m ² /dose (max 5 mg/dose) BID ⁺	1 – 28	⁺ Dose is BID. For example, if age < 18 years old, administer 2.4 mg/m ² /dose BID. The total daily dose is 4.8 mg/m ² /day, divided BID (maximum starting dose is 5 mg BID). ⁺ See Section 4.4.3 for dose titration guidelines.

Enter Cycle #:			Ht	cm	Wt	kg	BSA	m ²
Date Due	Date Given	Day	Axitinib mg AM and mg PM				Cycle 1 Studies	Cycles 2 – 26 Studies
Enter calculated dose above and actual dose administered below								
		1	mg	mg			a – r	a – r
		2	mg	mg				
		3	mg	mg				
		4	mg	mg				
		5	mg	mg				
		6	mg	mg				
		7	mg	mg				
		8	mg	mg			a*, c*, d – g	
		9	mg	mg				
		10	mg	mg				
		11	mg	mg				
		12	mg	mg				
		13	mg	mg				
		14	mg	mg				
		15	mg	mg			a, c – g	g
		16	mg	mg				
		17	mg	mg				
		18	mg	mg				
		19	mg	mg				
		20	mg	mg				
		21	mg	mg				
		22	mg	mg			a*, c*, d – g	
		23	mg	mg				
		24	mg	mg				
		25	mg	mg				
		26	mg	mg				
		27	mg	mg				
		28	mg	mg				s
		29	Begin next cycle on Day 29 or when criteria to begin cycle are met, whichever occurs later. See Section 4.4.3 .				* For patients < 18 years of age only.	

See [Section 5.0](#) for Dose Modifications for Toxicities. See [Section 7.0](#) for end of treatment evaluations.

4.4.2 Required Observations in Arm B: Axitinib

All baseline studies must be performed prior to starting protocol therapy unless otherwise indicated below.

- a. Physical Exam: Prior to each cycle, and additionally during Cycle 1:
For patients < 18 years old, perform weekly
For patients ≥ 18 years old, perform every other week
- b. Height/Weight: Prior to each cycle.
- c. CBC/diff/platelets: Prior to each cycle, and additionally during Cycle 1:
For patients < 18 years old, perform weekly
For patients ≥ 18 years old, perform every other week
- d. Creatinine, bilirubin: Prior to each cycle, weekly during Cycle 1 only.
- e. Electrolytes, BUN, Ca²⁺, PO₄, Mg²⁺: Prior to each cycle, weekly during Cycle 1 only.
- f. AST/ALT/Albumin: Prior to each cycle, weekly during Cycle 1 only.
- g. Blood Pressure: Every other week, weekly during Cycle 1 only. For pediatric patients who are dose escalated, weekly monitoring for the first cycle at the higher dose will be required (See [Section 5.2.5.4](#))
- h. PT/INR: Prior to every odd-numbered cycle (e.g., Cycles 1, 3, 5, etc.).
- i. TSH: Prior to every odd-numbered cycle (e.g., Cycles 1, 3, 5, etc.).
- j. Urinalysis/Urine Protein/Creatinine: Prior to Cycles 1, 2, 3, and then prior to every odd-numbered cycle (e.g., Cycles 5, 7, 9 etc.).
- k. Lipase: Prior to each cycle.
- l. Pregnancy Test: Female patients of childbearing potential require a negative pregnancy test within 72 hours prior to starting treatment and then prior to every odd-numbered cycle (e.g., Cycles 3, 5, 7, etc.); sexually active patients must use an acceptable method of birth control.
- m. ECG: Prior to every 4th cycle starting Cycle 1 (e.g., Cycles 1, 5, 9, etc.).
- n. MUGA or ECHO: Prior to every 4th cycle starting Cycle 1 (e.g., Cycles 1, 5, 9, etc.).
- o. GFR or Creatinine Clearance: Prior to every 4th cycle starting Cycle 1 (e.g., Cycles 1, 5, 9, etc.). See [Appendix VII](#) for GFR calculation.
- p. Immune biomarkers (patient consent is required): Before treatment initiation and before Day 1 of Cycles 2, 3, and 9 (within 72 hours prior to Day 1 dosing), and within 3 weeks after the last dose of study treatment. See [Section 15.2.1](#) for complete details.
- q. Tumor Tissue (patient consent is required): Before treatment initiation and at any time tumor tissue is obtained (i.e. surgery). See [Section 15.2.2](#) for complete details.
- r. Specimens for Banking (patient consent is required): See [Section 15.2.3](#) for complete details.
- s. Tumor Imaging: After Cycles 2, 4, 6, 9, 12, and then every 4 cycles; at relapse. See [Section 16.2](#) for complete details.

This listing only includes evaluations necessary to answer the primary and secondary aims. OBTAIN OTHER STUDIES AS REQUIRED FOR GOOD CLINICAL CARE.

Comments

(Include any held doses, or dose modifications)

4.4.3 Treatment Details – Arm B: Axitinib

IMPORTANT: Arm B is closed to new patients as of Amendment 2A. For patients who were enrolled and randomized to Arm B prior to Amendment 2A, please refer to the treatment details below.

Each cycle lasts 28 days (4 weeks). Absent disease progression or unacceptable toxicity, patients may continue on protocol therapy for up to 2 years duration or completion of 26 cycles, whichever comes first.

Criteria to start each cycle: ANC \geq 1000/ μ L, platelet count \geq 75,000/ μ L without transfusion support. See [Section 5.0](#) for other requirements related to any toxicities.

Axitinib: PO

Days: 1 – 28

Dose: Age-based dosing as follows:

If \geq 18 years old: 5 mg/dose BID*

If $<$ 18 years old: 2.4 mg/ m^2 /dose BID (maximum starting dose of 5 mg/dose)*. See [Appendix IV](#) for axitinib dosing nomogram and titrations.

NOTE: Dose is BID. For example, if $<$ 18 years old administer 2.4 mg/ m^2 /dose BID. The total daily dose is 4.8 mg/ m^2 /day, divided BID (maximum starting dose is 5 mg BID).

Axitinib should be taken by mouth twice daily approximately 12 hours apart. Axitinib may be taken with or without food. Tablets should be administered whole and intact with a glass of water or other liquid; do not crush or cut tablets. If a dose is missed or vomited, the patient/subject should not try to repeat or “catch up” the dose. The next dose should be given at the next regularly scheduled time point.

Axitinib will be distributed by the Division of Cancer Treatment and Diagnosis (DCTD), NCI. Do not use commercial supply.

